7.2.1. Fresh Biopsy Patient Adverse Events

Summary of adverse events, not necessarily TEAEs, experienced within 7 days of fresh biopsy will be generated by SOC, PT, and CTCAE grade. A listing of AEs experienced within 7 days of biopsy will also be generated for patients who have undergone fresh biopsy.

7.2.2. Infusion-related Reactions

A summary table of TEAEs under the Standard MedDRA Query (SMQ) with the keyword hypersensitivity (narrow) or PT terms ‘flushing’, ‘erythema’, ‘erythema of eyelid’ occurring within 3 days after any infusion will be generated by SOC, PT, and CTCAE grade. A listing will also be generated.

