5.5.5. Potential Infusion-related Reactions

Some patients treated with IV infusions of therapeutic drugs have experienced concurrent IRR (see CTCAE Version 5.0). The signs and symptoms may vary and include, for example, headache, fever, facial flushing, pruritus, myalgia, nausea, chest tightness, dyspnea, vomiting, erythema, abdominal discomfort, diaphoresis, shivers, lightheadedness, hypotension, palpitations, and somnolence. Anaphylaxis might occur at any time during an infusion. Before any infusion is started, appropriate medical personnel, medication (eg, epinephrine, inhaled beta agonists, antihistamines, and corticosteroids), and other required resources to treat anaphylaxis must be readily available. In general, Investigators should manage acute allergic or hypersensitivity reactions according to Institutional practices. General guidelines for the management of acute IRRs and for subsequent retreatment are provided in [Table 7](#). Delayed IRRs may occur; therefore, patients should be advised to seek immediate medical treatment if symptoms newly develop and/or recur after discharge from clinic.

Table 7: Management Guidelines for Potential Infusion-related Reactions

Infusion Reaction CTCAE v5.0 Severity Grade	Management
Grade 1: Mild, transient reaction	
 Maintain infusion rate unless progression of symptoms to \geq Grade 2; if symptoms worsen, refer to guidelines below. Promethazine (or equivalent) 150 mg PO per day (Q4h) PRN for nausea Diphenhydramine (or equivalent) 25-50 mg PO or IV PRN Methylprednisolone (or equivalent) 125 mg IV PRN
Grade 2: Moderate	
 Interrupt infusion and disconnect infusion tubing from patient Promethazine (or equivalent) 150 mg PO per day (Q4h) PRN for nausea Diphenhydramine (or equivalent) 25-50 mg PO or IV PRN Acetaminophen (or equivalent) 650 mg PO PRN Methylprednisolone (or equivalent) 125 mg IV PRN After recovery from symptoms, resume the infusion at 50% of the previous rate and if no further symptoms appear, gradually increase rate until infusion is completed. For subsequent dosing in future cycles, patients should be pre-medicated with Dex (or equivalent) 8 mg PO BID the day before drug administration and acetaminophen (or equivalent) 650 mg PO and diphenhydramine (or equivalent) 25-50 mg PO 30-60 min before dosing.

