Grade 3: Severe, prolonged reaction not rapidly responsive to symptomatic medication and/or brief interruption of infusion; recurrence of symptoms after initial improvement; hospitalization indicated for clinical sequelae OR Grade 4: Life-threatening consequences, urgent intervention indicated	
 Immediately stop infusion and disconnect infusion tubing from patient. Administer diphenhydramine (25-50 mg) IV (or equivalent) Administer IV steroids (methylprednisolone (or equivalent) up to 0.5 mg/kg Q 6h) to treat ongoing reaction and prevent recurrence Administer bronchodilators (nebulized albuterol/salbutamol, 2.5-5 mg in 3 mL of saline or equivalent) as medically indicated Administer normal saline as medically indicated Administer epinephrine (0.2-0.5 mL of a 1:1000 dilution (0.2-0.5 mg) SQ or IM) as medically indicated. Epinephrine should only be used if all other treatment methods fail to manage the IRR. Advise patient to seek emergency treatment and notify Investigator/clinic if the infusion-related symptoms recur after discharge from clinic. Report as an SAE (see Section 8.1.1.2). Permanently discontinue study medication treatment

Abbreviations: BID = twice a day; CTCAE = common terminology criteria for adverse events; Dex = dexamethasone; IM = intramuscular; IRR = infusion-related reaction; IV = intravenously; PO = orally; PRN = as needed; SAE = serious adverse event; SQ = subcutaneous.

Document ID: CLIN-00067	Title: IMGN853-0419 Clinical Study Protocol	Version: 2.0
Legacy ID: 26587		Approved Date: 12/22/202

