8.2. Adverse Events

8.2.1. Reporting Serious Adverse Events

Any SAE, regardless of relationship to study medication, which occurs in a patient from the time of study informed consent until 30 days after the last study treatment, must be recorded by the clinical site on an SAE report form. Only SAEs which are considered related to a study procedure (ie, blood draw or fresh tumor biopsy) will be captured during the pre-screening period, ie, from the time of signing the pre-screening consent (if one is utilized) until the signing of the main study informed consent, or until the patient is determined to be a screen failure. The SAE must also be recorded in the clinical trial database, including the Investigator's assessment regarding the relationship of the SAE to the study drug. The Investigator will promptly supply all information requested by the Sponsor (or contract research organization [CRO]) regarding the SAE.

The Investigator must submit the SAE Report Form to ImmunoGen Pharmacovigilance (or designee). This form must be completed and submitted within 24 hours of the Investigator's learning of the event using the contact information printed on the SAE form and contained within the SAE form completion instructions. Follow-up information must also be submitted using a new SAE Report Form.

When reporting SAEs, the following additional points should be noted:

- The underlying diagnosis or syndrome should be reported as the primary SAE term, rather than the signs or symptoms (signs and symptoms may be described in the narrative).
- An event term of "Death" should not be reported as an SAE, but rather be recorded as an outcome of a specific SAE term. Initially, the event term of "death" can be used until the actual cause of death is known. If an autopsy was performed, the autopsy report should be provided.

It is the responsibility of the Sponsor to ensure that each Investigator receives a copy of any suspected unexpected serious adverse reaction (SUSAR) report (CIOMS/MedWatch) regarding the study drug and that the report is submitted to the appropriate national regulatory agencies.

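### The infusion-related reaction table in SAP 7.2.2 does not name the infusion-related reaction diagnosis, so a diagnosed reaction is included only if the SMQ holds its term and onset is within 3 days

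*SAP*

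**What the plan says.** SAP 7.2.2, headed Infusion-related Reactions, selects events by coded term and time. An event qualifies if it is among "TEAEs under the Standard MedDRA Query (SMQ) with the keyword hypersensitivity (narrow) or PT terms" "flushing’, ‘erythema’, ‘erythema of eyelid". The time limit is in the same sentence: "occurring within 3 days after any infusion will be generated by SOC, PT, and CTCAE grade". A listing accompanies the table. The section names no preferred term for the reaction itself and does not use the investigator's identification of an event as an IRR. SAP 7.2 leaves the dictionary at MedDRA 24.0 or later.

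Protocol 5.5.5 describes the reaction clinically, by reference to CTCAE v5.0 and an open list of examples: "The signs and symptoms may vary and include, for example, headache, fever, facial flushing, pruritus, myalgia, nausea, chest tightness, dyspnea, vomiting, erythema", followed by seven more. It adds "Delayed IRRs may occur; therefore, patients should be advised to seek immediate medical treatment", without giving a time limit. Table 7 sets management by the grade of the reaction. Its Grade 3/4 row requires an SAE report and ends with "Permanently discontinue study medication treatment".

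For SAEs, protocol 8.2.1 says "The underlying diagnosis or syndrome should be reported as the primary SAE term, rather than the signs or symptoms". The same section has the SAE entered in the clinical trial database as well, and SAP 7.2 takes its AE summaries and listings from that database.

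**The concern.** The protocol has sites recognise, grade, manage and, when severe, report an event called an infusion-related reaction. The SAP table of that name retrieves hypersensitivity terms plus three added terms, so the two rules need not pick out the same events. Serious reactions are the ones most clearly meant to carry the diagnosis term, and the SAP search does not name that term.

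What is at stake is whether the table means what its title says. The focused safety groupings in SAP 7.2 are ocular events, peripheral neuropathy and pneumonitis, so 7.2.2 is the only output dedicated to IRRs. A reader looking for the IRR rate of an intravenous antibody conjugate will take it from there. If a diagnosed reaction is absent, that rate no longer describes the event the protocol asked sites to report.

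**Working it through.** Neither document states an IRR figure, so there is nothing to reproduce. The check sets the two rules side by side.

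**Inputs.** From SAP 7.2.2: the narrow hypersensitivity SMQ, three added preferred terms and a 3-day window. From protocol 5.5.5: the example signs, the CTCAE reference and the statement on delayed reactions. From Table 7: the grading and the Grade 3/4 actions. From protocol 8.2.1: the term convention for SAEs. From the protocol synopsis: approximately 75 patients.

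**Step 1: the signs.** Protocol 5.5.5 lists 17 examples: headache, fever, facial flushing, pruritus, myalgia, nausea, chest tightness, dyspnea, vomiting, erythema, abdominal discomfort, diaphoresis, shivers, lightheadedness, hypotension, palpitations and somnolence. Two of them (flushing, erythema) match a term the SAP adds by name. The other 17 − 2 = 15 enter the table only if the narrow SMQ contains the corresponding term.

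**Step 2: the diagnosis.** A reaction reported as an IRR carries a diagnosis term, which the SAP does not name. It too enters only through the SMQ, whose contents are not in the documents.

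**Step 3: the cases.**

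| How the event is coded | Onset after infusion | In the SAP 7.2.2 table? |
|---|---|---|
| IRR diagnosis | within 3 days | only if the SMQ version used holds the term |
| IRR diagnosis | later than 3 days | no, whatever the SMQ holds |
| Flushing, erythema or erythema of eyelid | within 3 days | yes |
| Another sign | within 3 days | only if the SMQ holds that term |
| Any sign | later than 3 days | no |

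The first two rows are the point. For an event the investigator has diagnosed as an IRR, inclusion rests on two conditions that the protocol does not impose.

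**Step 4: where such an event still appears.** SAP 7.2 provides all TEAEs by SOC and PT, serious TEAEs, Grade 3 or higher TEAEs, TEAEs leading to drug withdrawal, and a listing of all AEs. A treatment-emergent Grade 3/4 reaction coded to the diagnosis would be serious and at least Grade 3, and under Table 7 it would end treatment. It would therefore appear under its own term in each of these. A lower-grade diagnosed reaction would appear in the all-TEAE tables and the AE listing.

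**Step 5: size.** One patient among 75 is 1/75 = 1.3%, so each patient left out lowers the dedicated rate by 1.3 percentage points. The number left out cannot be derived. The protocol's summary of changes, explaining why blood draws after Grade 2 or higher reactions were dropped, says IRRs are not common in earlier studies of this drug.

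**The case against.** The strongest objection is that the main route to a loss depends on a source nobody can check here. If the narrow SMQ in the version used already contains the diagnosis term, every diagnosed reaction starting within 3 days is captured. This stands, and it limits the conclusion to what is guaranteed. It does not remove the point, because the SAP leaves the dictionary version open and the 3-day cut-off applies whatever the SMQ contains.

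A restricted search is also defensible. Several of the listed signs are non-specific, and nausea alone was reported in 51% of MIRV patients in the earlier Phase 3 study (protocol 1.5.2). Putting all 17 signs into the table would swamp it. That is right, and the fix does not do so. The list is also illustrative, so it would be wrong to say that the protocol formally defines IRRs more broadly than the SAP does.

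Three stronger readings are tempting and are not supported:

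- A reader might infer that Grade 3/4 reactions will go unreported. They would still appear in the serious, Grade 3 or higher and withdrawal tables.
- A reader might infer that the IRR rate will be too low by some stated amount. The documents give no IRR count from which to derive one, and what they do say is that the events were uncommon.
- A reader might infer that the added terms bring in unrelated events. The protocol itself lists facial flushing and erythema as signs of an IRR and recognises delayed reactions, so the documents give little basis for that charge.

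Finally, the diagnosis-term convention in 8.2.1 is stated for SAEs. A non-serious reaction may be recorded by its symptoms, and naming the diagnosis term would not recover it.

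**Conclusion.** The point holds as a gap in what the dedicated output guarantees. Under SAP 7.2.2 a diagnosed IRR is certain to be in the IRR table and listing only if the SMQ version used contains its term and onset is within 3 days. The first condition cannot be checked from the documents. The second sits uneasily with the protocol's statement on delayed reactions. The documents support saying that diagnosed reactions can be absent, not that they will be.

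Only one descriptive table and its listing are affected. The ORR test, the futility rule and the key secondary endpoint do not use them, and protocol 8.1.1.3 names no adverse events of special interest. The size is 1.3 points per patient, assuming 75 treated, with an unknown and probably small number of patients. This is a minor-priority improvement, worth making because it removes the dependence on SMQ contents and on the window for the very event the table is named after.

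**What to change.** In SAP 7.2.2, keep the existing search and its 3-day window as one component. Add a second component: any TEAE coded to the preferred term Infusion related reaction, or whose reported AE term is an infusion-related reaction, regardless of SMQ membership and of the 3-day window. Show the two components as separate rows, and carry both into the listing.

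This uses AE terms already collected, so it needs no new CRF field. It costs a sentence in the SAP and one more term in the table program. The reported IRR rate may rise slightly. If the SMQ already holds the preferred term, the change adds only reactions starting after 3 days.

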7.3. Clinical Laboratory Results

Laboratory test results (including hematology, coagulation, serum chemistry, and urinalysis) and abnormal laboratory values will be presented in data listings. Urinalysis and coagulation are collected at screening only.

CTCAE Version 5.0 laboratory grades will also be presented. CTCAE grades will be derived based on laboratory results and will not factor in clinical evaluations.

Shift tables summarizing the changes from baseline in severity of laboratory grades will be provided for laboratory parameters graded according to CTCAE Version 5.0. Grade 3 or higher laboratory values will be summarized based on the worst grade observed during MIRV treatment or within 30 days of the last dose.

Clinically significant values in liver function tests (LFTs) will be summarized by the following categories, using the maximum value while on MIRV. The denominator for the summaries will be the number of patients who had at least 1 non-missing value during treatment. The categories for each test are not mutually exclusive:

- Aspartate aminotransferase (AST).
 - $> 3 \times \text{ULN}$.
 - $> 5 \times \text{ULN}$.
 - $> 10 \times \text{ULN}$.
 - $> 20 \times \text{ULN}$.
- Alanine Aminotransferase (ALT).
 - $> 3 \times \text{ULN}$.
 - $> 5 \times \text{ULN}$.
 - $> 10 \times \text{ULN}$.
 - $> 20 \times \text{ULN}$.
- AST or ALT.
 - $> 3 \times \text{ULN}$.
 - $> 5 \times \text{ULN}$.
 - $> 10 \times \text{ULN}$.
 - $> 20 \times \text{ULN}$.
- Total bilirubin (TBILI).
 - $> \text{ULN}$.
 - $> 2 \times \text{ULN}$.
- Alkaline phosphatase (ALP).
 - $> 1.5 \times \text{ULN}$.
- (AST or ALT) and TBILI (concurrent).
 - AST or ALT $> 3 \times \text{ULN}$ and TBILI $> 1.5 \times \text{ULN}$.
 - AST or ALT $> 3 \times \text{ULN}$ and TBILI $> 2 \times \text{ULN}$.
- (AST or ALT) and ALP and TBILI (concurrent).
 - AST or ALT $> 3 \times \text{ULN}$ and ALP $< 2 \times \text{ULN}$ and TBILI $> 2 \times \text{ULN}$.

Here, concurrent means that all the associated LFTs must be from the same visit. In addition, worst postbaseline grade for LFTs will be summarized. Because baseline values of LFTs are already taken into account in CTCAE V5.0, shift table from baseline to worst postbaseline grade will not be generated for LFTs.

Results from pregnancy tests will be provided in listings.

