- f. Therapy changed due to toxicity in the absence of progression will be considered part of the same line (ie, not counted independently)

10. Patients must have completed prior therapy within the specified times below:

- a. Systemic antineoplastic therapy within 5 half-lives or 4 weeks (whichever is shorter) prior to first dose of MIRV
- b. Focal radiation completed at least 2 weeks prior to first dose of MIRV

11. Patients must have stabilized or recovered (Grade 1 or baseline) from all prior therapy-related toxicities (except alopecia)

12. Patients must have completed any major surgery at least 4 weeks prior to first dose of MIRV and have recovered or stabilized from the side effects of prior surgery prior to first dose of MIRV

13. Patients must have adequate hematologic, liver and kidney functions defined as:

- a. Absolute neutrophil count (ANC) $\geq 1.5 \times 10^9/L$ ($1500/\mu L$) without granulocyte colony-stimulating factor (G-CSF) in the prior 10 days or long-acting white blood cell (WBC) growth factors in the prior 20 days
- b. Platelet count $\geq 100 \times 10^9/L$ ($100,000/\mu L$) without platelet transfusion in the prior 10 days
- c. Hemoglobin $\geq 9.0 \text{ g/dL}$ without packed red blood cell (PRBC) transfusion in the prior 21 days
- d. Serum creatinine $\leq 1.5 \times$ upper limit of normal (ULN)
- e. Aspartate aminotransferase (AST) and alanine aminotransferase (ALT) $\leq 3.0 \times$ ULN
- f. Serum bilirubin $\leq 1.5 \times$ ULN (patients with documented diagnosis of Gilbert syndrome are eligible if total bilirubin $< 3.0 \times$ ULN)
- g. Serum albumin $\geq 2 \text{ g/dL}$

14. Patients must be willing and able to sign the informed consent form (ICF) and to adhere to the protocol requirements

15. Women of childbearing potential (WCBP) must agree to use highly effective contraceptive method(s) while on MIRV and for at least 3 months after the last dose

16. WCBP must have a negative pregnancy test within the 4 days prior to the first dose of MIRV

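### Three liver-test rows in SAP 7.3 (bilirubin above ULN, bilirubin above 2 x ULN in Gilbert patients, ALP above 1.5 x ULN) can be met by patients whose values never change, because the table has no baseline reference

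*SAP*

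**What the plan says.** SAP 7.3 sets the rule for the liver table: "Clinically significant values in liver function tests (LFTs) will be summarized by the following categories, using the maximum value while on MIRV". On who is counted it adds: "The denominator for the summaries will be the number of patients who had at least 1 non-missing value during treatment". The table has 18 rows:

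- AST, ALT, and AST or ALT: >3, >5, >10 and >20 x ULN each (12 rows).
- Total bilirubin: >ULN and >2 x ULN (2 rows).
- ALP: >1.5 x ULN (1 row).
- Joint, all tests from the same visit: AST or ALT >3 x ULN with bilirubin >1.5 x ULN; the same with bilirubin >2 x ULN; and the latter with ALP <2 x ULN (3 rows).

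Worst post-baseline CTCAE grade is also summarized for liver tests, and all laboratory results are listed. The liver tests are left out of the shift tables given for other graded parameters. The reason offered is: "Because baseline values of LFTs are already taken into account in CTCAE V5.0, shift table from baseline to worst postbaseline grade will not be" produced for them.

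Protocol 3.1.1, criterion 13, sets the entry limits. AST and ALT may be at most 3.0 x ULN. Bilirubin may be at most 1.5 x ULN, but "patients with documented diagnosis of Gilbert syndrome are eligible if total bilirubin" is below 3.0 x ULN. There is no ALP limit.

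Protocol 10.2 promises a summary of shifts from baseline in blood chemistry and makes no exception for liver tests, which belong to the chemistry panel in Protocol Table 8. SAP section 9, which records departures from the protocol, lists only the change from 4 to 6 tumor assessments.

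**The concern.** The trial has one arm, so no control group shows how often these cut-offs are crossed without the drug. The patient's own baseline is the only internal reference, and the table does not use it. Where a cut-off lies inside the range that eligibility allows, a patient can be counted in a table labelled clinically significant without any change on treatment. The counts for bilirubin and ALP then mix three things that a reader cannot separate: values already raised at entry, ordinary fluctuation over repeated tests, and rises on MIRV.

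The SAP's reason for dropping the shift table concerns CTCAE grades. The x ULN rows are not grades, so that reason does not supply the baseline reference they lack.

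**Working it through.** The plan states no figure on this point, so there is none to reproduce.

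**Step 1. Row cut-off against entry limit (x ULN).** Entry limits are from Protocol 3.1.1, criterion 13; rows are from SAP 7.3.

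| Row | Entry limit | Met by a qualifying value alone? | Rise needed from the limit |
|---|---|---|---|
| AST/ALT >3 | ≤3.0 | No; the limits touch | any |
| AST/ALT >5, >10, >20 | ≤3.0 | No | >1.67, >3.33, >6.67-fold |
| Bilirubin >1 | ≤1.5 | Yes | none |
| Bilirubin >2, no Gilbert | ≤1.5 | No | >1.33-fold (2/1.5) |
| Bilirubin >2, Gilbert | <3.0 | Yes | none |
| ALP >1.5 | none | Yes | none |
| All joint rows | AST/ALT ≤3.0 | No; AST or ALT >3 is required | any, in AST or ALT |

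So 3 of 18 rows can be met by entry status alone, one of them only in Gilbert patients. A Gilbert patient may enter above 1.5 or 2 x ULN and so already meet the bilirubin part of every joint row. AST or ALT passing 3 x ULN then completes the first two; the third also needs ALP <2 x ULN.

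**Step 2. One patient, no drug effect.** With a constant usual value m, log-normal variation with log-SD s, k tests and cut-off c:

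p = 1 − Φ(ln(c/m)/s), and P(maximum > c) = 1 − (1 − p)^k.

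The values of s and k are assumptions. With k = 8 and s from 0.10 to 0.25:

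- ALT, m = 2.5, c = 3. At s = 0.10, p = 0.034 and P = 24%. At s = 0.25, p = 0.233 and P = 88%.
- Gilbert patient, m = 1.8, c = 2: P = 72% to 96%. At m = 2.6, P is about 100%.
- Bilirubin, m = 1.1 to 1.3, c = 1: about 100%.

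**Step 3. All patients, no drug effect.** In a Monte Carlo run, patients' usual values are log-normal. One screening value must satisfy the entry limit where there is one, and the maximum of k on-treatment values is compared with the cut-off. Every distribution figure is assumed. Gilbert patients are not modelled separately.

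| | Bilirubin >ULN | ALP >1.5 x ULN |
|---|---|---|
| Population median (x ULN) | 0.4-0.5 | 0.7-0.8 |
| Between-patient log-SD | 0.35-0.45 | 0.35-0.45 |
| Within-patient log-SD | 0.15-0.25 | 0.08-0.12 |
| Tests on treatment | 6 or 10 | 8 |
| Counted with no effect | 2.2%-24.4% | 3.4%-15.8% |
| – of which above the cut-off at screening | 0.6-6.6 points | 1.6-8.5 points |

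The bilirubin rate is at least 5% in 14 of 16 scenarios. For 75 patients the ranges are 75 × 0.022 = 1.7 to 75 × 0.244 = 18.3 patients (bilirubin), and 75 × 0.034 = 2.6 to 75 × 0.158 = 11.9 patients (ALP). Similar runs for AST/ALT >3 x ULN give less than 0.5% of all patients.

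**Step 4. Protocol against SAP.** Protocol 10.2 commits to blood chemistry shifts, Table 8 places AST, ALT, bilirubin and ALP in that panel, SAP 7.3 removes the liver shift table, and SAP section 9 is silent. The departure is explained in 7.3 but not recorded where departures are listed.

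**The case against.** The strongest defence is that a fixed-multiple table is a deliberately sensitive screen and was never meant to show change. It attaches no causality, test or decision to any row. Fifteen of 18 rows cannot be met by qualifying entry values. Joint rows require all components at the same visit, so separate maxima are not combined. Worst CTCAE grade is also tabulated, and with about 75 patients each flagged case can be read against its listing. The waiver sentence speaks of a grade shift table, so the SAP does not use CTCAE to justify the x ULN rows. The simulated rates span more than tenfold for bilirubin because the assumptions drive them.

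Most of this stands and limits the point. A reader might infer that the table's cut-offs are simply the entry limits, so that patients with no drug effect are reported as liver signals, or that a Hy's-law-type row can be met at entry. The documents do not support either. For AST/ALT the entry rule is ≤3.0 and the row is >3, every joint row needs AST or ALT above that limit, and the SAP does not call any counted patient a drug signal.

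The defence does not answer the three overlapping rows. The grade summary is a different tabulation; that it accounts for baseline is the SAP's own statement, not checked here. Listings allow case reading but do not change the published counts. Nor does the defence explain why a promised summary was dropped without an entry in section 9.

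**Conclusion.** The point holds in limited form. Bilirubin >ULN, ALP >1.5 x ULN and, for Gilbert patients, bilirubin >2 x ULN can be met with no change on treatment, and a Gilbert patient can enter with the bilirubin part of the joint rows already met. The overlap follows from the documents alone. Its size does not: the 2-24% and 3-16% no-effect rates rest wholly on assumed medians, variability and numbers of tests, and the documents give no baseline liver-test distribution and no count of Gilbert patients. No rate is claimed for the joint rows. Entry status explains only part of the no-effect counts; in the simulation the rest comes from taking a maximum over repeated tests.

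The unrecorded departure from Protocol 10.2 needs no assumption. The consequence is confined to descriptive safety tables, and the ORR test is unaffected. The change is worth making because the trial has no control arm and the data are already collected.

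**What to change.** In SAP 7.3:

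1. Keep the existing all-patients rows.
2. Add one table of baseline x ULN category by worst on-treatment x ULN category for AST, ALT, bilirubin and ALP, using the SAP 4.2 baseline. This also restores the Protocol 10.2 commitment for these four tests.
3. For each bilirubin and ALP row, add the number of patients who meet it on treatment but not at baseline.
4. For any joint-row case, show the patient's baseline values and Gilbert status. Do not exclude patients whose bilirubin criterion was already met at baseline: that would hide a genuine ALT rise in a Gilbert patient.
5. If the grade shift table stays omitted, record the departure in SAP section 9 and state that the CTCAE reason applies to grades only.

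The cost is SAP wording, one extra table and a few added counts, with no new data and no burden on patients or sites. The count in item 3 has a limit: it removes patients already above the cut-off at entry, but not those who cross it through ordinary variation. For the latter, the table in item 2 shows the starting level.
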